## **5 ENROLLMENT, DISCONTINUATION AND WITHDRAWAL OF STUDY PARTICIPANTS**

### **5.1 Inclusion Criteria**

Individuals must meet *all* of the following inclusion criteria to be eligible for participation in this study.

1. Must provide written informed consent (signed and dated), and any authorizations required by law, and be able to comply with all study requirements.

2. Males or females,  $\geq 18$  years of age at the time of informed consent.
3. Females must have a negative serum pregnancy test at screening and a negative urine pregnancy test on their first dosing day.
4. Females must not be or planning to be pregnant or lactating during the study. Females must be post-menopausal (confirmed by follicle-stimulating hormone [FSH] test for subjects whose last menstrual cycle was within the last 2 years before screening), abstinent, in a monogamous same sex relationship, surgically sterile or, if of child bearing potential, must use two acceptable methods of contraception with at least one being a barrier method throughout their study participation and for at least 6 months following the last dose of study treatment. Acceptable methods of contraception include oral, injectable or implantable hormonal contraception, intrauterine device, or medically-confirmed vasectomized partner.
5. Males must be surgically sterile, abstinent, or if engaged in sexual relations with a female of child-bearing potential, must be using two acceptable methods of contraception with at least one being a barrier method for at least 6 months following the last dose of study treatment. Contraception for male subjects could include a condom and a highly effective second method during and for at least 6 months after the last dose of study treatment.
6. Investigator feels that the subject is likely to form keloids in the upper back/shoulder area after punch biopsy based on a history of a high frequency of keloid formation (history of  $\geq 10$  keloids), or a history of large keloids ( $\geq 4$  cm).
7. Must have bilateral  $2\text{ cm} \times 2\text{ cm}$  areas, where skin punch biopsy may be performed in the upper back/shoulder region and can be covered by clothing, that are free of keloids, acne, striae or other skin pathologies or complications (e.g., tattoos, excessive hair) that may obstruct the ability to evaluate the biopsy sites.
8. Subject is currently clinically stable and is likely to remain clinically stable for a minimum of 14 months from screening.
9. Subject is not anticipated to require systemic corticosteroids during participation in the study.
10. Must be able to communicate effectively with study personnel.

## **5.2      Exclusion Criteria**

Individuals who meet *any* of the following exclusion criteria are not to be enrolled in this study.

1. Recent history of alcoholism (within the past 1 year).

2. History of drug abuse or use of illicit drugs (such as cocaine, methamphetamines, or heroin) within 1 year prior to screening. Subjects must also agree to refrain from illegal drug use during the study.
3. Systemic use of steroids within 4 weeks of Day 1, or local use of steroids within 1 week of Day 1.
4. An active or uncontrolled infection at screening or Day 1.
5. Positive at the time of screening for human immunodeficiency virus (HIV), Hepatitis B (surface antigen), or Hepatitis C.
6. Liver dysfunction, as defined by alanine aminotransferase (ALT), aspartate aminotransferase (AST), bilirubin, or alkaline phosphatase  $> 1.5 \times$  upper limit of normal (ULN) at screening or Day 1.
7. Renal dysfunction defined as serum creatinine  $> 2$  mg/dL at screening or Day 1.
8. Clinically significant anemia, neutropenia, or thrombocytopenia at screening or Day 1.
9. History of bleeding diathesis or coagulopathy.
10. Genetic disorders that predispose to keloids. These include, among others, Ehlers-Danlos syndrome, Ullrich congenital muscular dystrophy, and Rubenstein-Taybi syndrome.
11. Prior malignancies within the past 3 years (allowing squamous cell and basal cell carcinomas with free margins at excision, or other malignancies considered cured by surgical resection).
12. Presence on ECG of QT interval corrected for heart rate using Fridericia's formula (QTcF)  $> 450$  msec or  $> 480$  msec if concomitant bundle branch block, at screening or Day 1.
13. Use of an investigational small molecule drug during the 30 days prior to screening or use of an investigational oligonucleotide or biologic drug during the prior 90 days.
14. History of allergy or severe adverse reaction to an oligonucleotide.
15. Unwillingness to comply with study procedures, including follow-up, as specified by this protocol, or unwillingness to cooperate fully with the Investigator.
16. Clinically significant abnormalities in medical history, physical examination, or laboratory values that, in the opinion of the Investigator, would make the subject unsuitable for inclusion in the study.

## **5.3 Participant Discontinuation or Withdrawal**

### **5.3.1 Reasons for Participant Discontinuation or Withdrawal**

Subjects may withdraw their consent to participate in the study at any time for any reason without prejudice to their future medical care by the physician or at the institution. If a subject withdraws consent, the date and stated reason for consent withdrawal should be documented.

Subjects meeting any of the following criteria should discontinue study treatment:

- Unacceptable AE(s) or failure to tolerate study treatment;
- Changes in the subject's condition or development of an intercurrent illness that renders the subject unsuitable for further study treatment in the judgment of the Investigator;
- Withdrawal of consent;
- Pregnancy (treatment will be discontinued but study observations may continue);
- Subject is lost to follow-up;
- Discretion of the Investigator;
- Termination of the study by the Sponsor.

### **5.3.2 Procedures for Participant Discontinuation or Withdrawal**

Wherever possible, the tests and evaluations listed for the post-treatment evaluation period should be carried out and an effort should be made to continue follow-up. The Sponsor should be notified of all study withdrawals through the designated electronic case report forms (eCRFs) in a timely manner.

Additional subjects may be enrolled in a given cohort (up to a total of 16 subjects in a cohort), if fewer than 10 subjects complete study participation through 24 weeks for reasons other than the safety or tolerability of study treatment, or if dosing is not completed per protocol for an individual subject for reasons other than the safety or tolerability of study treatment.

## **6 STUDY PRODUCTS**

### **6.1 Study Product(s) Management**

#### **6.1.1 Acquisition**

MRG-201 will be supplied by the Sponsor and sent to clinical study sites. The study sites will provide placebo comparator (0.9% sodium chloride injection, United States Pharmacopeia [USP]).

#### **6.1.2 Formulation, Appearance, Packaging, and Labeling**

The MRG-201 Drug Product is manufactured according to current Good Manufacturing Practice (cGMP) regulations for use in clinical trials.

The MRG-201 Drug Product is supplied as a sterile solution for injection. The Drug Product is formulated in an isosmotic phosphate buffer, pH  $7.4 \pm 0.5$ , corresponding to 66 mg/mL of the active moiety. The Drug Product is packaged in single-use glass vials with a rubber closure and an aluminum flip-off overseal, each containing 0.3 mL of a clear to slightly yellow liquid formulation.

#### **6.1.3 Storage and Stability**

The MRG-201 Drug Product is stored at  $-20 \pm 5^{\circ}\text{C}$ , protected from light.

#### **6.1.4 Accountability**

The investigator is responsible for ensuring adequate accountability of all used and unused study treatment. All drug supplies and associated documentation will be reviewed and verified by the Clinical Research Associate (CRA). Unused material cannot be disposed of until approval is obtained from the CRA. The study site is responsible for the disposal and/or destruction of all unused study treatment supplies, according to the site's standard operating procedures. If the site cannot dispose of these materials, arrangements should be made between the site and Sponsor's representative for destruction or return of the unused study treatment supplies.

## **6.2 Dosage, Preparation and Administration of Study Products**

### **6.2.1 Dose and Regimen**

As outlined in [Section 4.2](#), each subject will receive injections with MRG-201 and placebo around the site of two separate 6-mm punch biopsies. The treatment for each wound site will be

randomized (left versus right) and blinded but consistent throughout dosing. MRG-201 and placebo will each be administered as four 20- $\mu$ L injections around one wound site, with subjects receiving approximately 5.3 mg of MRG-201 active moiety on each dosing day (approximately 1.3 mg per 20- $\mu$ L injection).

Study treatment injections for subjects receiving 6 doses in their initial treatment cycle will be administered on Days 1, 3, 5, 8, 10, and 12 of the first cycle of study dosing. A second cycle of 6 study treatment injections will be administered for subjects who exhibit evidence of keloid formation (defined as meeting a score of 1 or 2 on the mVSS and having an appearance consistent with an area likely to form a keloid according to investigator judgement) within 12 weeks after initiation of the first cycle of study dosing and following the initial 29-day treatment and assessment period. The treatment regimen for the second cycle of study dosing will be the same as for the first cycle, i.e., an initial dose on Day 1 followed by additional doses on Days 3, 5, 8, 10, and 12, with follow-up visits at Days 19 and 29 after the re-start of dosing.

Subjects in additional optional cohorts may receive blinded study treatment injections on Days 1, 3, 5, 8, 10, 12, 15, 17, 19, 22, 24, and 26 and will not be given a second cycle of dosing.

#### **6.2.2 Method of Assignment to Treatment**

Subjects will be enrolled sequentially, starting with the first study cohort. The treatment for each wound site will be randomized (left versus right), such that all subjects will receive both MRG-201 and placebo in a double-blinded fashion.

#### **6.2.3 Dose Preparation and Administration**

MRG-201 must be prepared in accordance with local pharmacy practices using aseptic technique. Complete details on the preparation and administration of study treatment are provided in a separate Pharmacy Manual.

#### **6.2.4 Assessment of Treatment Adherence**

All study treatments will be administered at the investigational site by qualified study personnel.

#### **6.2.5 Dose Modifications or Delays**

Allergic events and/or injection-related toxicities should be managed according to institutional guidelines. If institutional guidelines are not available, the following recommendations apply. Rash, pruritus, urticaria and wheezing may be treated with diphenhydramine hydrochloride and/or steroids as clinically appropriate. Anaphylaxis or anaphylactoid signs or symptoms may

be treated with steroids and/or epinephrine as clinically indicated. Subjects should be treated in a facility equipped for cardiopulmonary resuscitation. Injection-related reactions (fever, rigors) should be treated per institutional guidelines but may be treated with acetaminophen and diphenhydramine hydrochloride.

### **6.3 Prior and Concomitant Medications**

All medications (including over-the-counter medicines, herbal treatments, supplements, and vitamins) administered 30 days before the first administration of study treatment (Day 1) through the end of the study will be recorded on the eCRF, using generic names when possible.

Systemic use of steroids is not permitted within 4 weeks of Day 1, and local use of steroids is not permitted within 1 week of Day 1. Systemic or local corticosteroids are not permitted during the first 12 weeks of study conduct. If an adverse event requires corticosteroid use, the investigator must contact the Medical Monitor to discuss the intervention and plans for continued subject participation. After 12 weeks, corticosteroids may be allowed after discussion with the Medical Monitor.

## **7 STUDY PROCEDURES**

The procedures and assessments that are outlined in this section will be performed at the time points specified by study visit in [Section 8](#) and summarized in [Appendix A](#) (Schedule of Events, First Cycle of Study Dosing) and [Appendix B](#) (Schedule of Events, Second Cycle of Study Dosing).

Written informed consent must be provided by each subject prior to the initiation of any study procedure or assessment that is not part of standard of care.

### **7.1 Clinical Assessments**

#### **7.1.1 Medical History**

Medical history will be recorded at screening. Any ongoing conditions and signs and symptoms observed prior to first dose of study treatment should be recorded as medical history.

#### **7.1.2 Vital Signs**

Vital signs (blood pressure, heart rate, respiratory rate, and body temperature) will be measured at screening and at the time points indicated in [Appendix A](#), [Appendix B](#), and [Appendix C](#).

### **7.1.3 Physical Examination**

A complete physical examination will be performed by trained medical personnel at screening and on Day 1 of each cycle of study dosing. Brief symptom-directed physical examinations should be performed at the subsequent time points specified in [Appendix A](#), [Appendix B](#) and [Appendix C](#). Weight will be documented only at screening, on Days 12 and 85 of the first cycle of study dosing (Day 26 and 85 if receiving 12 doses of blinded study treatment) and Day 12 of the second cycle of study dosing (if applicable), and at the end of the study (Day 365).

### **7.1.4 Prior and Concomitant Medications**

All medications (including over-the-counter medicines, herbal treatments, supplements, and vitamins) administered 30 days before the first administration of study treatment through the end of the study will be recorded.

## **7.2 Safety Assessments**

### **7.2.1 Adverse Events**

AEs will be assessed at each study visit by direct observation and subject interviews. The severity of AEs will be evaluated using the NCI CTCAE, version 5.0. All AEs that occur from initiation of study treatment through 30 days after the last dose of study treatment must be recorded, regardless of causal assessment to study treatment.

### **7.2.2 Clinical Laboratory Assessments**

Blood or urine samples will be collected for the following clinical laboratory measurements at screening to determine eligibility and predose at each time point indicated in [Appendix A](#), [Appendix B](#), and [Appendix C](#). Clinical laboratory assessments do not need to be performed on Day 1 of the study if screening laboratory measurements were performed within 3 days prior to Day 1.

- Hematology
- Clinical chemistry
- Urinalysis (including microscopy)

In addition, screening for HIV, hepatitis B, and hepatitis C will be performed during screening. Female subjects who are not surgically sterile or have had last menstrual period > 2 years from screening date will also undergo FSH testing during screening to confirm menopause.

### **7.2.2.1 *Pregnancy Test***

Female subjects must have a negative serum pregnancy test at screening and negative urine pregnancy tests at the subsequent time points specified in [Appendix A](#) and [Appendix B](#). A positive pregnancy test will result in immediate discontinuation of study treatment; however, study assessments will continue to evaluate study endpoints. All pregnancies will be followed through to outcome.

### **7.2.3 *Electrocardiograms***

Single 12-lead ECGs will be performed at screening and on Days 1 (predose), 2, and 12 (predose) of each cycle of study dosing (or Day 26, predose, in subjects receiving 12 doses of blinded study treatment in the first cycle), as specified in [Appendix A](#), [Appendix B](#) and [Appendix C](#). Electrocardiogram parameters to be evaluated include the RR, QT, QRS, and PR intervals. In addition, Fridericia's formula should be used to calculate the QT interval corrected for heart rate (QTcF). Abnormal ECG measurements will be recorded as AEs only if they are considered to be clinically significant by the investigator.

## **7.3 *Pharmacokinetic Sampling***

Plasma samples to measure MRG-201 concentrations will be collected on Days 1, 2, 12 and 13 (or Days 1, 2, 26, and 27 for subjects receiving an initial 26-day treatment cycle ) of the first cycle of study dosing at the pre- and postdose time points specified in [Appendix A](#) and [Appendix C](#). Voided urine samples for PK analyses will also be collected on Day 1 and Day 12 (or Day 26 for cohorts dosing for 4 weeks) predose and 3 hours postdose, and Day 2 and Day 13 (or day 27 for cohorts dosing for 4 weeks).

[figure not shown]

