### 3.2.5 Pharmacokinetic Endpoints

- Plasma concentration of MRG-201 will be assessed at multiple time points on Day 1 and Day 12 (or Day 26 for cohorts dosing for 4 weeks), and at single time points on Day 2 and Day 13 (or Day 27 for cohorts dosing for 4 weeks). Voided urine samples for PK analyses will also be collected on Day 1 and 12 (or Day 26 for cohorts dosing for 4 weeks) predose and 3 hours postdose, and Day 2 and Day 13 (or day 27 for cohorts dosing for 4 weeks).

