#### **8.2.6 Day 12**

- Obtain vital signs (blood pressure, heart rate, respiratory rate, and body temperature).
- Perform a brief, symptom-directed physical examination (including documentation of weight).
- Perform a single 12-lead ECG (predose).

- Collect blood (predose) for the following:
  - Hematology;
  - Clinical chemistry;
  - Antibody analysis;
  - PK (1 hour [ $\pm$  10 minutes], 2 hours [ $\pm$  15 minutes], and 3 hours [ $\pm$  15 minutes] postdose).
- Collect urine for PK 3 hours after dose ( $\pm$  1 hour).
- Collect urine (predose) for urinalysis and pregnancy test (females).
- Perform physician assessment of keloid formation and volume.
- Assign mVSS and POSAS scoring ([Fearnonti et al 2010](#), see [Appendix D](#) and [Appendix E](#)).
- Administer intradermal study treatments.
- Review and record AEs and concomitant medications.
- Note: Biopsy wound sites are to be photographed at the time the investigator suspects a keloid may be forming, at the time of observation of an unconfirmed keloid, and at the time of keloid confirmation.

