#### **11.4.5 Analysis of Exploratory Endpoint: Pharmacokinetics**

PK parameters ( $C_{max}$ ,  $T_{max}$ , apparent half-life [ $t_{1/2}$ ], apparent volume of distribution of the terminal phase [ $V_z/F$ ], apparent clearance [ $Cl/F$ ], and  $AUC$  extrapolated to infinity [ $AUC_{0-\infty}$ ]) will be derived from plasma concentrations of MRG-201 using the actual sampling times. Concentration data and all PK parameters will be listed by subject and summarized descriptively per dose. Standard algorithms of the non-compartmental PK analysis program, WinNonLin software, will be used for these analyses.

Individual plasma concentration versus actual time profiles for each subject and treatment, as well as the mean ( $\pm$  standard deviation) plasma concentration versus scheduled time profiles for each dose level, will be presented graphically.

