- m) A voided urine sample will be collected on Day 1 and 12 predose and 3 hours postdose, Day 2 and 13 (24  $\pm$  4 hours after Day 1/12 dosing).
- n) Photography of biopsy wound sites will be performed post-biopsy on Day 1. In addition to the indicated time points, wound sites will be photographed at the time the investigator suspects a keloid may be forming, at the time of observation of an unconfirmed keloid, and at the time of keloid confirmation (predose if coinciding with a dosing day). Refer to the Study Manual for detailed instructions.
- o) End-of-study assessments will be performed on Day 365 or at the final visit for subjects who discontinue treatment early (if the subject has not withdrawn consent).

**Appendix B. Schedule of Events for Second Cycle of Dosing with MRG-201 and/or Placebo (6 Doses after Initial Treatment Cycle)**

Study Procedure	Monthly Visit for Keloid Identification	Day 1 a	Day 2	Days 3 and 5	Day 8	Day 10	Day 12	Day 19 ( $\pm 2$ days)	Day 29 ( $\pm 3$ days)	Subsequent Visits, Every 4 Weeks ( $\pm 7$ days) k	Day 365/End of Study ( $\pm 7$ days) l
Keloid Identification	X									See Appendix A for a complete list of time points and assessments to be performed	See Appendix A for a complete list of assessments to be performed
Vital Signs		X	X	X	X	X	X	X	X		
Physical Examination b		X			X		X	X	X		
Weight		X					X				
Pregnancy Test c		X							X		
12-lead ECG d		X	X				X				
Laboratory Assessments e		X	X		X				X		
Study Treatment Injections f		X		X	X	X	X				
Physician Assessments for Keloid Formation and Volume g		X	X	X	X	X	X	X	X		
Modified Vancouver Scar Scale and POSAS		X			X		X	X	X		
Adverse Events h		X	X	X	X	X	X	X	X		
Concomitant Medications i		X	X	X	X	X	X	X	X		
Photography of Biopsy Sites j		X							X		

Abbreviations: AE = adverse event; aPTT = activated partial thromboplastin time; ECG = electrocardiogram; eCRF = electronic case report form; INR = international normalized ratio; PT = prothrombin time; SAE = serious adverse event

- a) Day 1 refers to the first dosing day for the second double-blind active treatment period. Procedures required for the regularly scheduled visit day must also be performed.
- b) Complete physical examination on Day 1; brief physical examination at all other time points.

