- h) Subjects will receive intradermal injections of MRG-201 and intradermal injections of placebo at each time point. Refer to the Study Manual for detailed instructions on intradermal injections – Biopsy Site Selection, Injection, and Brief Photography Instructions.
- i) All AEs, including SAEs, will be recorded from the time of administration of the first dose of study treatment on Day 1 until 30 days after the last dose of study treatment or the end of study visit, whichever occurs last. Treatment-related AEs ongoing at the follow-up visit should be followed to resolution or until the investigator considers them “chronic” or “stable.”
- j) All medications (including over-the-counter medicines, herbal treatments, supplements, and vitamins) administered 30 days before the first administration of study treatment (Day 1) until the end of study (Day 365) will be recorded on the eCRF.
- k) On Day 1 and Day 26, plasma for PK will be drawn at 1 hour ( $\pm$  10 minutes), 2 hours ( $\pm$  15 minutes), and 3 hours ( $\pm$  15 minutes) after injection.
- l) On Day 2 and Day 27, plasma for PK will be drawn 24 ( $\pm$  4) hours after Day 1/Day 26 dosing.
- m) A voided urine sample will be collected on Day 1 and 26 predose and 3 hours postdose, and Day 2 and 27 (24  $\pm$  4 hours after Day 1/26 dosing).
- n) Photography of biopsy wound sites will be performed post-biopsy on Day 1. In addition to the indicated time points, wound sites will be photographed at the time the investigator suspects a keloid may be forming, at the time of observation of an unconfirmed keloid, and at the time of keloid confirmation (predose if coinciding with a dosing day). Refer to the Study Manual for detailed instructions.
- o) End-of-study assessments will be performed on Day 365 or at the final visit for subjects who discontinue treatment early (if the subject has not withdrawn consent).

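### PK urine is taken as six single voids with no volume or collection interval and no planned urine parameter, so as written it supports only detected-or-not statements

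*Combined protocol and SAP*

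**What the plan says.** Section 3.2.5 places urine under the pharmacokinetic endpoints: "Voided urine samples for PK analyses will also be collected on Day 1 and 12". Section 7.3 repeats this: "Voided urine samples for PK analyses will also be collected on Day 1 and Day 12". Footnote m of the schedules sets the times. For the 6-dose regimen (Appendix A) it reads "A voided urine sample will be collected on Day 1 and 12 predose and 3 hours postdose, Day 2 and 13", and for the 12-dose regimen (Appendix C) "A voided urine sample will be collected on Day 1 and 26 predose and 3 hours postdose, and Day 2 and 27". In both, the next-day sample falls 24 ± 4 hours after dosing. Each sample is one void.

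On the analysis side, Section 11.4.5 states that the PK parameters "will be derived from plasma concentrations of MRG-201 using the actual sampling times". It also says: "Concentration data and all PK parameters will be listed by subject and summarized descriptively per dose". Urine is not named there. The PK Analysis Set (11.3.3) is defined by having plasma data. Section 7.6 leaves the handling of urine to a separate Laboratory Manual.

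**The concern.** A urine concentration becomes an excreted amount only when multiplied by the volume produced over a known interval. The protocol fixes neither. The concentration in a single void depends on fluid intake and on the time since the last void as well as on the drug. Higher concentrations on Day 12 than on Day 1, or in one dose cohort than in another, could therefore reflect hydration alone. With about 10 completers intended per cohort (11.5), such variation would not reliably average out.

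At stake is modest but avoidable waste. Six samples per subject are collected under a named endpoint that has no parameter, no summary naming it and no analysis set. Neither safety nor the keloid endpoints are affected.

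**Working it through.** **Step 1: what is scheduled, and what Section 8 lists.** The plan gives no urine figure to reproduce, so the passages are set side by side. Days 12 and 13 apply to the 6-dose regimen, Days 26 and 27 to the 12-dose regimen.

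| PK urine sample | 7.3 and footnote m | Section 8, 6-dose | Section 8, 12-dose |
|---|---|---|---|
| Day 1 predose | yes | not listed (8.2.1) | not listed (8.4.1) |
| Day 1, 3 h | yes | not listed (8.2.1) | not listed (8.4.1) |
| Day 2 | yes | not listed (8.2.2) | listed (8.4.2) |
| Day 12 or 26 predose | yes | not listed (8.2.6) | not listed (8.4.6) |
| Day 12 or 26, 3 h | yes | listed, ± 1 h (8.2.6) | listed, ± 1 h (8.4.6) |
| Day 13 or 27 | yes | listed (8.2.7) | listed (8.4.7) |
| Total | 6 | 2 | 3 |

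The Day 12 list, for example, says only "Collect urine for PK 3 hours after dose". The ± 1 h window appears in 8.2.6 and 8.4.6 alone. Section 7.3 and footnote m give no window for the 3-hour void, and none is stated for Day 1. The predose void, which would open any 0-3 h interval, appears in no Section 8 list.

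**Step 2: what a recovery calculation needs.**

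- Amount excreted = urine concentration × urine volume over a defined interval.
- Fraction excreted = amount excreted / dose.
- Renal clearance = amount excreted / plasma AUC over the same interval.

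The dose is available: 4 injections × 0.020 mL × 66 mg/mL = 5.28 mg, in agreement with the stated 5.3 mg. Volume and interval are not. For renal clearance, 11.4.5 also lists only the AUC extrapolated to infinity, not one over the collection interval.

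**Step 3: one concentration, several possible amounts.** The documents give no void volume or urine concentration, so both are assumed. A concentration of 100 ng/mL implies:

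- 50 mL: 100 × 50 = 5,000 ng = 0.005 mg, and 0.005 / 5.28 = 0.09% of dose
- 200 mL: 0.020 mg, or 0.38% of dose
- 600 mL: 0.060 mg, or 1.14% of dose

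The range is 600 / 50 = 12-fold, from volume alone.

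**Step 4: one amount, several possible concentrations.** Assume urine flows of 0.5 to 4 mL/min over 180 minutes.

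- Low flow: 0.5 × 180 = 90 mL
- High flow: 4 × 180 = 720 mL
- Ratio: 720 / 90 = 8

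If 0.020 mg (20,000 ng) were excreted in that time, the concentration would be 20,000 / 90 = 222 ng/mL or 20,000 / 720 = 28 ng/mL. This 8-fold spread has nothing to do with the drug, and it applies directly to comparisons between days and between cohorts.

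**Step 5: what needs no volume.** Whether drug or a metabolite is detectable in a void, before or after dosing, is answered by the concentration itself, subject to the assay limit.

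**The case against.** The strongest reply is that quantitative recovery is being imputed to the sponsor. The objective is a general characterization of the pharmacokinetics (3.1.3), the study tests no formal hypothesis (11.2), and no section makes amount excreted, fraction excreted or renal clearance an aim. That is correct, and it is why the point is minor.

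A reader might go further and infer that the urine samples yield nothing interpretable. The documents do not support that. A single void can show whether drug or metabolites reach urine, and Section 2.1.3.1 leaves open whether the metabolites seen in animals also form in humans. The protocol does not say that the urine serves this question, but it could.

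A reader might also infer that recovery can never be calculated. That is not established either. The Laboratory Manual (7.6) could require volumes, and the fuller SAP announced in 11.1 could add a urine summary. The 11.4.5 sentence on listing concentration data does not exclude urine. What stands is that neither document alone would close the gap. A volume in the manual would not supply the analysis missing from 11.4.5, and a later SAP could not recover volumes that were never measured.

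Finally, it would be tempting to claim that a 0-3 h pool captures a particular share of the drug. A simple half-life calculation assumes instant absorption and counts elimination by every route. Section 2.1.3.1 reports animal plasma peaks between 15 minutes and 2 hours, and rapid metabolism. No capture figure is claimed here.

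**Conclusion.** The point holds in a limited form. From the plan as written, the six PK urine samples per subject support qualitative statements only. Amount excreted, fraction excreted and renal clearance cannot be derived, and comparisons of concentration across days or cohorts are confounded by dilution. The 8-fold and 12-fold spreads illustrate the size of that confounding. They rest entirely on assumed flows and volumes, whereas the absence of a volume, an interval and a urine parameter is plain from the text.

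Separately, and without any assumption, Section 8 conflicts with 7.3 and Appendices A and C. A site working from the visit lists would take two of the six samples in the 6-dose regimen and three of six in the 12-dose regimen.

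This is an inexpensive improvement to an exploratory endpoint, not a threat to the trial's conclusions.

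**What to change.** 1. In 7.3 and in footnote m of Appendices A and C, for Day 1 and Day 12 (or 26): have the subject empty the bladder at the predose void, pool all urine from dosing to the 3-hour void, and record total volume and the start and stop times. Recorded times also deal with the ± 1 h window, because the actual interval is then known.
2. In 11.4.5, add amount excreted and percent of dose excreted over 0-3 h, and report the 24-hour void as detected or not detected. Describe the percentage as a share of the administered dose. With the low bioavailability seen nonclinically (at most 20%, Section 2.1.3.1), it is not a share of what was absorbed.
3. Reconcile the visit lists in 8.2.1, 8.2.2, 8.2.6, 8.4.1 and 8.4.6 with 7.3 and the appendices, so that the predose void and the pooled collection appear where sites will look for them.

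If the sponsor wants only qualitative information, the minimum is to say so in 3.2.5 and 11.4.5, and still carry out step 3.

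The cost is small: a measuring container, handling instructions for pooled urine, and eCRF entries for volume and two clock times. No visit or assay is added to the schedule in 7.3, since plasma is already drawn at 1, 2 and 3 hours after dosing. The downside is that a missed void loses that interval.
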